2. INTRODUCTION

This SAP provides the detailed methodology for summary and statistical analyses of the data collected in study A4091063. This document may modify the plans outlined in the protocol; however, any major modifications of the primary endpoint definition or its analysis will also be reflected in a protocol amendment.

2.1. Study Objectives

Primary Objective:

- *Evaluate the long-term safety of tanezumab 10 mg and 5 mg SC administered every 8 weeks (7 administrations).*

Secondary Objective:

- *Demonstrate the long-term analgesic efficacy of tanezumab 10 mg and 5 mg SC administered every 8 weeks (7 administrations).*

2.2. Study Design

This is a randomized, double-blind, active-controlled, multicenter, parallel-group Phase 3 study of the safety and efficacy of tanezumab when administered by SC injection for up to 56 weeks in subjects with chronic low back pain. Subjects will be randomized to 1 of 3 treatment groups in a 1:1:1 ratio. Treatment groups will include:

[figure not shown]
- 1. Placebo SC matching tanezumab administered at an 8-week interval (total of 7 times) plus celecoxib 100 mg twice a day (BID) to be administered orally for 56 weeks.*
- 2. Tanezumab 5 mg SC administered at an 8-week interval (total of 7 times) plus placebo matching celecoxib to be administered orally BID for 56 weeks.*
- 3. Tanezumab 10 mg SC administered at an 8-week interval (total of 7 times) plus placebo matching celecoxib to be administered orally BID for 56 weeks.*

The study is designed with a total duration (post randomization) of up to 80 weeks and will consist of three periods: Screening (up to 37 days; includes a Washout Period and an Initial Pain Assessment Period), Double-blind Treatment (56 weeks) and Follow-up (24 weeks).

The total sample size will be approximately 200 subjects (170-220 subjects, approximately 66 subjects [56-73 subjects] per treatment group). However, it is acceptable to randomize more than 220 subjects from the safety perspective as described below because primary objective is to evaluate the long-term safety.

The period of interest for most safety results is the treatment period. Selected safety results will be provided separately for the safety follow-up period and for the combined overall study period comprising the treatment and safety follow-up periods.

Figure 1. Study Schematic

3. ENDPOINTS AND BASELINE VARIABLES: DEFINITIONS AND CONVENTIONS

3.1. Primary Endpoints

Safety Measures

- *Adverse events.*
- *Standard safety assessments (safety laboratory testing [chemistry, and hematology], vital signs).*
- *Orthostatic (supine/standing) blood pressure assessments.*
- *Survey of Autonomic Symptoms (SAS) scores.*
- *Electrocardiogram (ECG, 12-lead) assessments.*
- *Joint Safety adjudication outcomes.*
- *Total joint replacements.*
- *Neurologic examination (Neuropathy Impairment Score [NIS]).*
- *Anti-drug antibody assessments (ADA).*
- *Physical examinations.*
- *Outcome of Consultation*

The details of the safety endpoints are described in [Section 3.5](#).

3.2. Secondary Endpoints

Efficacy-Related Endpoints

- *Change from Baseline to Weeks 1, 2, 4, 8, 12, 16, 24, 32, 40, 48, 56 and 64 in average Low Back Pain Intensity (LBPI) score as measured by an 11-point Numeric Rating Scale (NRS).*
- *Change from Baseline to Weeks 2, 4, 8, 16, 24, 32, 40, 48, 56 and 64 in the Roland-Morris Disability Questionnaire (RMDQ) total score.*
- *Change from Baseline to Weeks 2, 4, 8, 16, 24, 32, 40, 48, 56 and 64 in Patient's Global Assessment of Low Back Pain.*
- *Cumulative distribution of percent change from Baseline in average LBPI score to Weeks 16, 24 and 56.*

- Cumulative distribution of percent change from Baseline in RMDQ score to Weeks 16 and 56.
- *Response as defined by a $\geq 30\%$, $\geq 50\%$, $\geq 70\%$ and a $\geq 90\%$ reduction from Baseline in weekly average LBPI score derived from the subject diary at Weeks 16, 24, 40 and 56.*
- *Change from Baseline to Weeks 2, 4, 8, 16, 24, 40, 56 and 64 in the Brief Pain Inventory-short form (BPI-sf) scores for Worst Pain, Average Pain, Pain Interference Index (composite function score), Pain Interference with General Activity, Pain Interference with Walking Ability, Pain Interference with Sleep, and Pain Interference with Normal Work.*
- *The BPI-sf Pain interference index is calculated as the mean of the seven BPI-sf Pain interference items (question 5a to g), being Pain interference with General Activity; Mood; Walking Ability; Normal work; Relations with other people; Sleep; Enjoyment of life.*
- *Chronic Low Back Pain Responder Index analysis (composite endpoint of average LBPI score, Patient's Global Assessment of Low Back Pain, and RMDQ total score) at Weeks 16, 24, 40 and 56.*

For the definition of the Chronic Low Back Pain Responder Index, a responder is defined as:

- A reduction of $\geq 30\%$ in weekly average LBPI from baseline to that week, and
- A decrease of $\geq 30\%$ in Patient Global Assessment of low back pain from baseline to that week, and
- No worsening (increase) in Roland-Morris Disability Questionnaire total score from baseline to that week.
- *Treatment Response: Improvement of ≥ 2 points in Patient's Global Assessment of Low Back Pain at Weeks 16, 24, 40 and 56.*
- *Euro Quality of Life Health State Profile (EQ-5D-5L™) dimensions and overall health utility score at Baseline, Weeks 16 and 56.*
- *Work Productivity and Activity Impairment Questionnaire: Low Back Pain (WPAI:LBP) change from Baseline to Week 16, 56 and 64, in the percent work time missed due to chronic low back pain, percent impairment while working due to chronic low back pain, percent overall work impairment due to chronic low back pain, and percent activity impairment due to chronic low back pain.*
- *Incidence of and time to discontinuation due to lack of efficacy.*

- *Usage of rescue medication (incidence, and number of days of usage) during Weeks 1, 2, 4, 8, 12, 16, 24, 32, 40, 48, 56 and 64.*
- *Usage of rescue medication (amount taken) during Weeks 1, 2, 4, 8, 12 and 16.*
- *Health Care Resource Utilization (HCRU) at Baseline, Weeks 64 and 80.*

Treatment Satisfaction Measures

- *Treatment Satisfaction Questionnaire for Medication v.II (TSQM) score at Weeks 16 and 56.*

The 11 questions of the TSQM are used to calculate the 4 endpoints of Effectiveness, Side Effects, Convenience and Global Satisfaction, each scored on a 0-100 scale with 100 being the best level of satisfaction. The calculation of these 4 parameters are described in [Appendix 2.3](#).

- *Patient Reported Treatment Impact Assessment-Modified (mPRTI) at Weeks 16 and 56.*

3.3. Tertiary Endpoints

- *Plasma tanezumab concentrations.*
- *Serum NGF assessments.*
- *Serum and urine osteoarthritis biomarker concentrations.*

3.4. Baseline Variables

Baseline variables are demographics, general and musculoskeletal specific medical history, Musculoskeletal baseline status, prior/current medication use, primary diagnosis and Quebec Task Force (QTF) category.

The method and definition of reporting windows including Baseline for assigning efficacy data to particular time points is described in [Appendix 2.1](#).

3.5. Safety Endpoints

3.5.1. Adverse Events

An adverse event is considered treatment emergent relative to a given treatment if:

- The event occurs for the first time during the effective duration of treatment and was not seen prior to the start of treatment, or
- The event was seen prior to the start of treatment but increased in severity during treatment.

A 3-tier approach will be used to summarize AEs. Under this approach, AEs are classified into 1 of 3 tiers. Different analyses will be performed for different tiers (See [Section 6.1.1](#)).

Tier-1 events: These are pre-specified events of clinical importance. Tier-1 events include syncope, bradycardia, orthostatic hypotension, anhidrosis, hypohidrosis.

Tier-2 events: These are events that are not Tier-1 but are “common”. A MedDRA PT is defined as a Tier-2 event with a frequency of $\geq 3\%$ in any treatment group.

Tier-3 events: These are events that are neither Tier-1 nor Tier-2 events, and will be summarized using standard Pfizer data standards tables, where all Adverse Events will be included (ie, Tier-3 AEs will not be shown separately).

The adverse events of Abnormal Peripheral Sensation (APS) are defined in the table below.

| | |
|------------------------------|------------------------------------|
| Allodynia | Neuritis |
| Axonal neuropathy | Neuropathy peripheral |
| Burning sensation | Paraesthesia |
| Carpal Tunnel Syndrome | Paraesthesia oral |
| Decreased Vibratory Sense | Peripheral sensorimotor neuropathy |
| Demyelinating polyneuropathy | Peripheral sensory neuropathy |
| Dysaesthesia | Polyneuropathy |
| Formication | Polyneuropathy chronic |
| Hyperaesthesia | Sensory disturbance |
| Hyperpathia | Sensory loss |
| Hypoaesthesia | Thermohypoaesthesia |
| Hypoaesthesia oral | Sciatica |
| Intercostal neuralgia | Tarsal Tunnel Syndrome |
| Neuralgia | |

Adverse Events of Sympathetic Nervous System are defined in the table below.

| | |
|--------------------------------------|-------------------------|
| Abdominal discomfort | Micturition urgency |
| Anal incontinence | Nausea |
| Anhidrosis | Nocturia |
| Blood pressure orthostatic decreased | Orthostatic hypotension |
| Bradycardia | Pollakiuria |
| Diarrhoea | Presyncope |
| Dizziness postural | Respiratory distress |
| Early satiety | Respiratory failure |
| Ejaculation delayed | Sinus bradycardia |
| Ejaculation disorder | Syncope |
| Ejaculation failure | Urinary hesitation |
| Heart rate decreased | Urinary incontinence |
| Hypertonic bladder | Vomiting |
| Hypohidrosis | |

The lists given above may be updated depending on any additional adverse events observed in any tanezumab study. There are a number of summaries based on these groupings of adverse events.

3.5.2. Laboratory Tests

Laboratory tests will be summarized according to Pfizer standards.

3.5.3. Orthostatic (supine/standing) Blood Pressure Assessments

The incidence of orthostatic hypotension at each visit, at the last visit and for any post-baseline incidence will be summarized. The definition of orthostatic hypotension to be summarized is:

- For patients with Baseline supine systolic Blood Pressure ≤ 150 mmHg:
 - Reduction in sBP (standing minus supine) ≥ 20 , OR
 - Reduction in dBP (standing minus supine) ≥ 10 .
- For patients with Baseline supine systolic Blood Pressure > 150 mmHg:
 - Reduction in sBP (standing minus supine) ≥ 30 , OR
 - Reduction in dBP (standing minus supine) ≥ 15 .

3.5.4. Survey of Autonomic Symptoms (SAS) Scores

The Survey of Autonomic Symptoms (SAS) is a 12 item (11 for females) questionnaire. From this the total number of symptoms (0-12 for males and 0-11 for females) will be calculated. Where a patient has a symptom then the impact of that symptom is then rated from 1 ('not at all') to 5 ('a lot'). The total impact score is calculated using this 1-5 scale, with 0 assigned where the patient does not have the particular symptom. The range for the total impact score is 0-60 for males and 0-55 for females.

3.5.5. Electrocardiogram (ECG, 12-lead) Data

Electrocardiogram data including PR, QRS, QT, QTcF, QTcB, RR intervals, and heart rate [HR] will be summarized according to Pfizer standards.

3.5.6. Joint Safety Adjudication Outcomes and Total Joint Replacements

The following adjudication outcomes and total joint replacement endpoints are defined.

- The composite endpoint consisting of adjudication outcomes of rapidly progressive osteoarthritis (type-1 or type-2), subchondral insufficiency fracture, primary osteonecrosis, or pathological fracture.

- The composite endpoint consisting of adjudication outcomes of rapidly progressive osteoarthritis (type-2 only), subchondral insufficiency fracture, primary osteonecrosis, or pathological fracture.
- Individual adjudication outcomes of rapidly progressive osteoarthritis (type-1 only), rapidly progressive osteoarthritis (type-2 only), rapidly progressive osteoarthritis (type-1 or type-2 combined), subchondral insufficiency fracture, primary osteonecrosis, and pathological fracture.
- Total joint replacements.
- Total joint replacements or any adjudication outcome (subjects who undergo total joint replacement plus subjects who have an adjudicated outcome of rapidly progressive osteoarthritis type-1 or type-2, subchondral insufficiency fracture, primary osteonecrosis, or pathological fracture whether they undergo total joint replacement or not).

3.5.7. Neurologic Examination (Neuropathy Impairment Score [NIS])

The Neuropathy Impairment Score (NIS) is the sum of scores over all 37 items from both the Left and Right side. Items 1-24 are scored on a 0-4 scale (0, 1, 2, 3, 3.25, 3.5, 3.75, 4) and items 25-37 are scored on a 0-2 scale (0, 1, 2). The possible range of the NIS is 0-244.

3.5.8. Anti Drug Antibody Assessments (ADA)

The assessments of ADA data as described in [Section 6.1.9](#) will be summarized.

3.5.9. Physical Examinations

The physical examination data as described in [Section 6.1.10](#) will be summarized.

4. ANALYSIS SETS

Data for all subjects will be assessed to determine if subjects meet the criteria for inclusion in each analysis population prior to unblinding and releasing the database and classifications will be documented per standard operating procedures.

4.1. Intent To Treat Analysis Set

The intent to treat (ITT) analysis set is the primary analysis set for efficacy and safety analyses. It consists of all randomized subjects who received at least one dose of SC (subcutaneously) study medication (either tanezumab or placebo). This analysis set is used in the presentations of all efficacy data, and all data listings, and labeled as the 'ITT Analysis Set' or 'ITT population'. Subjects will be assigned per the treatment they were randomized to.

This analysis set is expected to be the same as the safety analysis set. If a subject is treated without having been randomized, then the analysis sets will be different, and safety analyses will use this different safety analysis set (see [Section 4.2](#)). If the sets are the same, safety analyses may still refer to it as the 'Safety Population'.

4.2. Safety Analysis Set

The safety analysis set is defined as all subjects treated with tanezumab or placebo SC. This analysis set will be labeled as the ‘Safety population’ in the corresponding safety data analyses, summaries, and listings. Subjects will be assigned per treatment they actually received.

4.3. Other Analysis Sets

TJR (Total Joint Replacement) Subset Analysis Set: This analysis set includes all subjects who undergo total joint replacements of the hip, knee or shoulder during participation in the study.

4.4. Treatment Misallocations

If a subject was:

- Randomized but not treated with SC study medication, then that subject will be excluded from all efficacy and safety analyses.
- Treated but not randomized, then by definition that subject will be excluded from the efficacy analyses, but will be reported under the treatment they actually received for all safety analyses.
- Randomized but took incorrect treatment, then that subject will be reviewed on a case-by-case basis by the study team and a decision on potential changes related to the subject and on how to analyze the data will be made in a timely manner and prior to database release.

5. GENERAL METHODOLOGY AND CONVENTIONS

5.1. Hypotheses and Decision Rules

No formal hypotheses are to be tested.

5.2. General Methods

5.2.1. Analyses for Binary Data

Output will show the number and percentage of subjects in each response category, and the response rate and its 95% confidence interval (CI) will be calculated. The confidence interval of the response rate will be calculated based on Agresti & Coull method.

5.2.2. Analyses for Continuous Data

The descriptive statistics n, mean, median, standard deviation, minimum, maximum and 95% CI will be used to summarize the endpoints.

The analysis for change from baseline of aLBPI (average LBPI) will use mixed model ANCOVA with a fixed effect of treatment group, Baseline aLBPI as a covariate, and study site as a random effect. The analysis for change from baseline of RMDQ will use mixed model ANCOVA with a fixed effect of treatment group, Baseline score and Baseline aLBPI as covariates, and study site as a random effect. Change from baseline at each time point will be estimated using least squares means (LS means) with standard error (SE) and 95% CI.

Estimates of treatment differences between each tanezumab treatment group versus celecoxib group will also be done using least squares means (LS means) with SE and 95% CI. P-value will not be shown. Under the analysis using multiple imputation defined in [Section 5.3](#), the multiple ANCOVA results will be combined using standard methods (Little & Rubin, 2002),⁴ which are described in [Appendix 4.2](#).

5.2.3. Analyses for Categorical Data

Output will show number and percentage of subjects in each category.

5.2.4. Analyses for Time to Event Data

Survival curve estimates (time to 1st, 2nd, 5th, 10th and 25th percentiles, and minimum and maximum values) and a plot of the time to event will be shown using the Kaplan-Meier estimates. Only discontinuation up to the end of treatment period (Week 56 visit or early discontinuation) will be used in this analysis.

Any subject who discontinues for any other reason than lack of efficacy prior to the Week 56 visit uses censoring at the time of discontinuation. Imputation of time to event for completed subjects or discontinued subjects (for any reason) after the Week 56 visit uses censoring at the Week 56 visit time point.

5.3. Methods to Manage Missing Data

Missing values in standard summaries of AEs, lab values, vital signs and ECGs will be handled per Pfizer standard algorithms.

The summary of LBPI, RMDQ, PGA and BPI-sf will use multiple imputation for missing data (where the method for imputation will be dependent on the reason for missing data). As for PGA and BPI-sf, the imputation will be used only for Week 16 and Week 56 analyses. The imputation strategies are described in the following table. While the table describes the multiple imputation strategy specific for the Week 16 time point, it also applies to Week 56 time point, eg, ‘Week 56’ would be substituted for ‘Week 16’ in the table, to describe the Week 56 multiple imputation strategy.

| Type of Missing Data | Imputation Method |
|---|---|
| Missing data resulting from discontinuation of treatment due to Death, Adverse Events (AEs) or Insufficient Clinical Response or Patient’s Meeting Protocol-Specified Pain Criteria for Discontinuation prior to or during the Week 16 visit reporting window*. | Multiple imputations will be created by sampling from a normal distribution based on the subject’s baseline score and the standard deviation (over all treatment groups) of the observed efficacy data at Week 16 overall ITT subjects. This is a multiple imputation version of BOCF single imputation method. |
| Missing data for other reasons, ie, 
 • Subject did not discontinue on or before Week 16 (includes discontinuation for any reason after the end of the Week 16 visit reporting window*), | Multiple imputations will be created by sampling from a normal distribution based on the subject’s last score and the standard deviation (over all treatment groups) of the observed efficacy data at Week 16 over all ITT subjects. For example if last observation |

| | |
|---|---|
| 
 • Subject discontinued for a different reason prior to or during the Week 16 visit reporting window*. | 
for a subject is at Week 12, then the imputation sample for that subject is created using the subject’s Week 12 observation and the standard deviation of the Week 16 observations for all subjects. Note: a subject’s last observation may be the Baseline observation. This is a multiple imputation version of LOCF single imputation method.
 |
|---|---|

* See [Appendix 2.1](#) for a definition of the reporting windows.

The imputation of baseline-like data for subjects with missing data due to discontinuation due to Death, AE or LoE is intended to impute conservative efficacy values for those subjects who discontinue because of a reason that is considered to be a poor outcome for the subject, and so a poor outcome is imputed. For those subjects with missing data that is likely to not be related to treatment group, the intention is that missing data should be imputed based on a ‘missing at random’ assumption taking into account the subject’s previous available data.

One hundred imputed samples will be used in this analysis. In order to pre-define the analysis (and not to allow the results to change if run again), the following seeds will be used in the creation of the multiple imputed data: aLBPI: 1001-1100; RMDQ: 2001-2100; PGA-LBP: 3001-3100; BPI-sf scores for Worst Pain, Average Pain, Pain Interference Index (composite function score), Pain Interference with General Activity, Pain Interference with Walking Ability, Pain Interference with Sleep, and Pain Interference with Normal Work: 4001-4100. Imputed Week 16 and 56 data for the PGA-LBP will be rounded to integer scores in the range 1 to 5. Imputed Week 16 and 56 data for the aLBPI that are <0 and >10 will be truncated to 0 and 10, respectively.

Two additional methods will explore the sensitivity of the effect of missing data. The first method of Baseline Observation Carried Forward (BOCF) for missing data at Week 16 and 56 will impute the subject’s Baseline value for the Week 16 and 56 time point, respectively, and therefore a zero change from baseline. If a subject’s baseline data is also missing then that subject’s data remain missing for the post-baseline time point. The second method of Last Observation Carried Forward (LOCF) for missing data at Week 16 and 56 will impute the subject’s last observed data value for the efficacy endpoint. With LOCF, if a subject is missing all post-baseline efficacy data for a given efficacy endpoint, then baseline will be carried forward (if baseline is missing then the subject would have no contributing data to be included in the analysis).

As for LBPI and RMDQ, ANCOVA with covariates described in [Section 5.2.2](#) will be conducted for all time points up to week 56. Study site will be fitted as a random effect in the ANCOVA model. This analysis will use multiple imputation for missing data as described above. While the table describes the multiple imputation strategy specific for the Week 16 time point, it also applies to all other analysis time points, eg, ‘Week 2’ would be substituted for ‘Week 16’ in the above table, to describe the Week 2 multiple imputation strategy.

The responder endpoints will be summarized, using both BOCF and LOCF for missing data of the response endpoint at a particular time point. Imputation using BOCF will lead to the subject being assessed as a non-responder. In addition, a mixed BOCF/LOCF imputation for response endpoints will be used. In this analysis BOCF imputation (ie, a subject would be a non-responder) would be used for missing data due to discontinuation for reasons of lack of efficacy, patient's not meeting protocol-specified pain criteria, adverse event or death up to the time point of interest, and LOCF imputation would be used for missing data for any other reason.

Note, if Baseline is missing then the subject data for the change from Baseline will be set to missing for all efficacy analyses for that parameter. A subject who has a missing Baseline score will be missing for the response criteria for endpoints where the response is based on one parameter.

The CLBP-RI (Chronic Low Back Pain Responder Index) is based on 3 parameters (aLBPI, RMDQ and PGA-LBP). It is set to missing if any one out of these three parameters are missing at baseline or for the relevant post-Baseline timepoint (per its definition, a response can still be achieved if all three component parameters meet certain criteria).

For the RMDQ, any missing items are treated as the patient not having that symptom, and so not included in the RMDQ total score.

The BPI-sf Pain interference index score is calculated from the seven BPI-sf pain interference items. The composite index score is calculated as the mean of the non-missing items as long as ≥ 4 of the 7 items are non-missing, otherwise (≤ 3 items non-missing) the index score is missing.

For the analysis of the rescue medication endpoints while subjects are still in the study any missing data will be imputed by carrying forward the last recorded daily data up to Week 16 (LOCF daily data). Imputation using the daily data will occur up to the end of the last week when the subject is in the study (see [Appendix 2.1](#) for definitions of the last study day in each week). For example if a subject discontinues on study day 10, then data up to the end of Week 2 will be imputed in this way. The weekly scores for the rescue medication endpoints can then be calculated for each week the subject is in the study. Rescue medication endpoints are summarized using LOCF, and so the last weekly score for the rescue medication will be used for LOCF after the subject has discontinued from the study (note, imputation is taken from the last week with non-missing data and not necessarily from the last available study week, eg, if Week 8 is missing then Week 7 data can be used). The baseline observation will not be carried forward in the case where a post-baseline observation is not available for the LOCF imputation. In the example above, the subject who discontinued in Week 2 (Study Day 10) will have their Week 2 value used as the LOCF value for all Weeks 3-16. The BOCF imputation rule will not be used for the subject because rescue medication is collected during the Initial Pain Assessment Period only (days -5 to -1) and subjects should not be taking rescue medication within 48 hours of the Baseline visit (so part of day -2, and day -1), therefore Baseline rescue medication use is not an accurate reflection of subjects true Baseline use of rescue medication. Imputation of weekly diary data after Week 16 will use LOCF based on the last available weekly diary data score available. Imputation of weekly diary data after week 56 will not be performed.

The Baseline mean will be calculated using potential five values of the Initial Pain Assessment Period (IPAP). Note, for the weekly pain score, a pain score being carried forward with LOCF might not be a visit week assessment (eg, carry forward Week 3 for missing Week 4 data). For the purposes of the imputation analyses, where there is no post-baseline observation available to carry forward, then the baseline score carried forward will be the baseline average pain score, being the mean of the expected five pain scores in the baseline assessment period. If any of the baseline average pain scores are missing (or there are less than 5 pain scores) then the baseline is calculated over the remaining non-missing values.

For the analysis of NIS, the Baseline observation will not be carried forward in the case where a post-baseline observation is not available for the LOCF imputation.

For the other efficacy and safety analyses, the observed data (no imputation for missing data) will be summarized if not otherwise specified. Additional analyses will be performed in order to explore the sensitivity of the efficacy analysis results to missing data as described in this section.

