6.2. Secondary Endpoints

All analyses in this section use the ITT analysis set, if not otherwise specified. If not otherwise specified, the observed data (no imputation for missing data) will be summarized.

All efficacy assessments during the treatment period are made on the analysis windows defined in [Appendix 2.1](#). Using these windows we find the analysis window for a patient's last subcutaneous (SC) dose. Any data included in a window that is up to 8 weeks from this last SC dose window is 'on-treatment', and any data included in a window that is more than 8 weeks after the last SC dose window is off-treatment. Data in on-treatment analysis windows will be used in summaries and analyses, while data in off-treatment analysis windows will be excluded from all summaries and analyses of treatment period efficacy data, ie, up to Week 56.

Efficacy data collected via subject diary (aLBPI and rescue medication use) are collected daily or weekly, not at study visits. Diary efficacy data will be considered on-treatment if it is collected up to 84 calendar days after the last SC dose. Diary efficacy data collected more than 84 calendar days after the last SC dose will be considered off-treatment and excluded from summaries and analyses of treatment period efficacy data.

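### CLBP Responder Index: one missing component erases an observed failure, so LOCF can count a known non-responder as a responder

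*SAP*

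**What the plan says.** SAP 3.2 requires all three of the following for a CLBP-RI response:

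- a reduction of at least 30% "in weekly average LBPI from baseline to that week, and"
- on the global scale, a fall of at least 30% "in Patient Global Assessment of low back pain from baseline to that week, and"
- for function, an RMDQ total no higher at that time point than it was at baseline

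SAP 5.3 then gives the missing-data rule for the index: "It is set to missing if any one out of these three parameters are missing at baseline or for the relevant post-Baseline timepoint". A parenthesis follows, saying that "a response can still be achieved if all three component parameters meet certain criteria". This restates the definition and makes no exception for a component that has been observed and has failed.

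The same section summarises the responder endpoints "using both BOCF and LOCF for missing data of the response endpoint at a particular time point". In the mixed analysis, missing data after discontinuation for lack of efficacy, the pain criteria, an adverse event or death are scored as non-response. Otherwise "LOCF imputation would be used for missing data for any other reason".

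SAP 6.2.5 refers back to 5.3 for missing data and plots the index at Weeks 16, 24, 40 and 56 under mixed BOCF/LOCF. SAP Appendix 1 lists four versions of the analysis: observed, mixed BOCF/LOCF, BOCF and LOCF.

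**The concern.** The index is a conjunction. A subject whose global assessment has returned to baseline at Week 56 is a non-responder at Week 56, whatever the diary would have shown. The rule in SAP 5.3 discards that knowledge as soon as another component is absent.

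Two things follow on the literal text. Where LOCF applies, an earlier index value fills the gap, and if it was a response, a past success overwrites a present failure. In the observed-data table the subject leaves the denominator. SAP 5.3 says that its multiple imputation is meant to give conservative values to subjects with poor outcomes. Replacing an observed failure with an earlier success runs against that aim, and it reaches the one version of this endpoint that will be plotted.

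**Working it through.** The plan states no figure for this point, so there is nothing to reproduce. The check has four parts.

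**1. How often the rule discards a settled outcome (logic only).** Each component can pass, fail or be missing, giving 3 × 3 × 3 = 27 states.

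- States with nothing missing: 2 × 2 × 2 = 8. The rule therefore sets 27 − 8 = 19 states to missing.
- Of those 19, states with no observed failure: 2 × 2 × 2 − 1 = 7.
- States set to missing although an observed component has failed: 19 − 7 = 12.

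In all 12, non-response is certain. In none of the 19 is response certain. These are counts of logical states, not of subjects.

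**2. One hypothetical subject.**

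| | aLBPI | PGA-LBP | RMDQ | Index |
|---|---|---|---|---|
| Baseline | 7 | 3 | 12 | |
| Week 40 | 3 (−57%, pass) | 2 (−33%, pass) | 6 (pass) | Responder |
| Week 56 | missing | 3 (0%, fail) | 12 (pass) | Set to missing by SAP 5.3 |

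If the subject has not discontinued for a reason on the BOCF list, LOCF of the index carries the Week 40 result and Week 56 is reported as a response. LOCF of the components carries aLBPI 3, keeps the observed PGA failure and gives non-response. The two programs disagree.

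**3. Size per subject.** SAP 2.2 gives about 66 subjects per arm (56 to 73). One misclassified subject adds 1/66 = 1.5 points (1/56 = 1.8; 1/73 = 1.4).

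As an illustration, assume 26 true responders of 66 (39.4%) and 3 subjects with an observed failure and a missing component:

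- LOCF turns all three into responders: 29/66 = 43.9%.
- The observed-data table drops them: 26/63 = 41.3%.

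The 26 and the 3 are assumptions.

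**4. Where partly missing data come from.**

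- LBPI is a weekly diary item (Protocol 7.1.1). SAP Appendix 2.1 takes Week 16 from Days 106–112, normally one entry, so one missed entry makes the Week 16 index missing. A false response there also needs an index derived at an earlier visit (Week 2, 4 or 8), and the SAP does not say whether one is derived.
- After Week 16, aLBPI pools up to four weekly entries and uses what is available, so all four must be missed.
- PGA-LBP and RMDQ come from the same clinic visits, so a missed visit removes both and leaves the diary score alone.
- On-treatment rules: "Diary efficacy data will be considered on-treatment if it is collected up to 84 calendar days after the last SC dose", whereas clinic data count by analysis window. At target dosing days the cut-offs coincide with the ends of the clinic windows: 57 + 84 = 141 (Week 16), 113 + 84 = 197 (Week 24), 337 + 84 = 421 (Week 56). The only overlap is a boundary day; for example, Day 141 belongs to the Week 16 clinic window and the Week 24 diary interval. A larger mismatch needs off-schedule dosing. A Week 8 dose given on Day 64 lets diary data count to 64 + 84 = 148, inside the Week 24 diary interval (141–168), while Week 24 clinic data are excluded.

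**The case against.** The best defence is that LOCF may be meant to act on each component before the index is derived. SAP 5.3 speaks of carrying a pain score forward, and SAP 6.2.1 speaks of imputing aLBPI and then classifying response. On that reading the observed failure survives and the LOCF tables are correct. This is possible, but those passages concern aLBPI and none concerns the index. The sentence that governs responder endpoints points to the response endpoint, and SAP 6.2.5 adds nothing. Nor does this reading help the observed-data table.

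Second, LOCF of the index can also err downward: two observed passes and one missing component may be carried forward as non-response. That is true, but it is ordinary imputation of an unknown outcome. The 12 states above are known outcomes, and there the error can run only upward.

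Third, a complete-case table is a familiar convention. Partial data can establish non-response but never response, so adding known failures back moves the observed rate only downward. This is a fair reason to keep a complete-case version, provided the number of known failures left out is shown.

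Fourth, a reader might infer that the different on-treatment rules for diary and clinic data build in partial missingness. The coinciding cut-offs in the working do not support that; off-schedule dosing is a marginal source.

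**Conclusion.** The point holds for the LOCF analysis, the LOCF branch of the mixed analysis (and so the plot) and the observed-data table. The direction is upward, measured against a tabulation that keeps the observed failures. BOCF is unaffected, as is mixed handling of discontinuation for lack of efficacy, pain criteria, adverse event or death. A false response under LOCF requires three things: LOCF acting on the index, an earlier complete index that was a response, and a reason for missingness outside the BOCF list.

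The total effect cannot be sized. A reader might assume that 5–15% of subjects have a component missing and that 10–20% of those have relapsed on an observed one, giving 0.5 to 3 points. The documents support neither range; only the per-subject figure of 1.4 to 1.8 points follows from them.

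A reader might also take this for a key efficacy result. SAP 3.2 lists the index among many secondary endpoints without ranking, SAP 5.1 plans no hypothesis test, and SAP 6.2.5 asks for rates with confidence intervals by treatment. This is a matter of descriptive accuracy and reproducible programming, not of error rates. Priority is low.

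**What to change.** In SAP 5.3, replace the missing-data rule for the index with the following:

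- At each time point, score CLBP-RI as non-response if any observed component fails there.
- Set it to missing, and impute it where the analysis calls for that, only if no observed component fails and at least one is missing. A component without a baseline value counts as missing.
- State whether LOCF acts on the components or on the index and, if on the index, from which visits it may be carried.

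If a complete-case version of the observed-data table is kept, add a footnote per arm with the number of subjects left out who had an observed failure.

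The cost is two or three sentences in the SAP and one derivation line. No new data are needed. Under LOCF of the index, the change can only turn a wrongly carried response into non-response.
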